This Statistical Analysis Plan (SAP) describes the statistical methods to be used during the reporting and analysis of data collected under the ReActiv8-B Clinical Investigation Plan (CIP).

2. Scope

This SAP should be read in conjunction with the CIP and case report forms (CRFs). This version of the SAP has been developed with respect to the CIP version 950057, Rev A and updated per 950057, Rev B. Any further changes to the CIP or CRFs may necessitate updates to the SAP.

3. Primary Efficacy Objective

The Primary Efficacy Endpoint is a comparison of responder rates between Treatment and Control groups, where a “responder” is a Subject with $\geq 30\%$ reduction from baseline in average low back pain VAS without any increase from baseline in pain medication and/or muscle relaxants prescribed and taken in the two weeks prior to the Primary Endpoint Assessment Visit.

Note: The primary outcome measure is intended to assess the efficacy of 120 days of stimulation. Thus the visit for assessment of the primary outcome must occur no sooner than 120 days post randomization.

4. Secondary Efficacy Objectives

There are six specified secondary efficacy objectives. The first five objectives have associated endpoints and hypotheses and will be statistically tested at the Primary Endpoint Assessment Visit. The sixth objective, consisting of multiple endpoints, will be evaluated after the Outcome Post Crossover Visit but does not have associated statistical hypotheses.

1. Comparison of change from baseline in Oswestry Disability Index (ODI) between Treatment and Control groups at the Primary Endpoint Assessment Visit
2. Comparison of change from baseline in EQ-5D between Treatment and Control groups at the Primary Endpoint Assessment Visit
3. Comparison of Percent Pain Relief between Treatment and Control groups reported by the Subject at the Primary Endpoint Assessment Visit
4. Comparison of Subject Global Impression of Change at the Primary Endpoint Assessment Visit
5. Comparison of number of Subjects with Resolution of Low Back Pain (remitters or cure, defined as a VAS score $\leq 2.5\text{cm}$) at the Primary Endpoint Assessment Visit
6. Evaluation of changes in primary and secondary efficacy metrics in the Crossover group following the Outcome Post Crossover Visit.

5. Trial Design

The study is an international, multi-center, prospective, randomized, sham controlled, blinded trial with an adaptive statistical design. Subjects and investigators are blinded to treatment assignment, and the assessment of primary endpoint data is blinded. Subjects meeting all eligibility criteria who have been implanted with ReActiv8 will be randomized to either the Treatment Arm or the Control Arm. Randomization will be performed according to a random permuted block design stratified by clinical site with a 1:1 allocation ratio for Treatment vs. Control.

All Subjects are implanted with the ReActiv8, and then at the Randomization Visit are instructed to deliver stimulation for 60 minutes per day, in two 30-minute sessions (morning and evening). Subjects are randomized (1:1) to the Treatment or Control Arm at the Randomization Visit.

Subjects randomized to the Treatment Arm of the study will have ReActiv8 programmed to deliver stimulation at a Subject-appropriate level (The Treatment group). Determination of the Subject appropriate level is described in the Implant and Programming Manual. Subjects in the Treatment group may or may not feel muscle contraction during stimulation.

Subjects randomized to the Control Arm will have ReActiv8 programmed to deliver minimal stimulation (The Control group). Subjects in the Control group may or may not feel muscle contraction during stimulation.

All Subjects will have automatic electrical impedance measurement of electrodes performed immediately prior to each stimulation session.

IRB (or Ethics Committee) and FDA approval will be sought to enroll up to 800 Subjects, in up to 40 implanting sites to achieve an initial target of 116 randomized Subjects in the Intent to Treat (ITT) Cohort. An adaptive statistical design using one interim look when at least 50% of Subjects have completed the Primary Endpoint Assessment Visit, will be used for a potential sample size re-estimation.

A Subject is “enrolled” in the study at the time of informed consent. Subjects who are enrolled, meet the required inclusion and exclusion criteria, and continue consent will be scheduled for implant of the ReActiv8.

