Treatment Arm	ReActiv8 implanted and configured to deliver stimulation at a Subject-appropriate level and Subjects instructed to deliver stimulation in two 30-minute sessions per day (the Treatment group).
Control Arm	ReActiv8 implanted and configured to deliver minimal stimulation, and Subjects instructed to deliver stimulation in two 30-minute sessions per day (the Control group).
Randomization	Subjects meeting all eligibility criteria who have been implanted with ReActiv8 will be randomized post-implant to either the Treatment group or the Control group. Randomization will be performed according to a random permuted block design stratified by clinical site with a 1:1 allocation ratio for Treatment vs. Control.
Anticipated Sample Size	Initial estimate: 128 randomized Subjects implanted with ReActiv8 in the intent to Treat cohort of the study, plus up to 80 Subjects implanted in the Surgical Roll In group. An adaptive statistical design using a single interim look will be used for sample size re-estimation when at least 50% of the implanted Subjects have completed the Primary Endpoint Assessment Visit. Up to 800 Subjects will be enrolled to account for screen failures prior to implant, Surgical Roll In, drop outs, and possible increase in numbers for the intent to treat analyses after the interim look.
Anticipated Number of Sites	There will be up to 40 Investigational sites performing implants. Each site will have a Site Principal Investigator who may or may not be the implanting physician. One or more Sub-investigators per site (or affiliated site if the affiliated site has a different Ethics Committee or IRB) may be used for example for device implantation and Subject recruitment.

Surgical Training and Surgical Roll In	All physicians who will implant any portion of the system will be trained as outlined in the Training Strategy. Following training, up to the first two Subjects implanted by the same physician may be prospectively included in a Surgical Roll In group. Subjects included in the Surgical Roll In group will be randomized to Treatment or Control with a single group randomization, and be analyzed as a separate cohort (the Surgical Roll In Cohort).

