4.4. Study Size and Duration

A minimum of 116 evaluable Subjects is required to sufficiently power the primary endpoint. To allow for attrition, 128 Subjects will be randomized as part of the Intent to Treat Cohort. Up to 80 additional Subjects will be randomized as part of the Surgical Roll In phase as described below (assuming one implanting surgeon per site). Therefore, the total number of implanted and randomized Subjects will be up to 208. In order to account for screen failures prior to implant up to 800 Subjects will be enrolled. An adaptive statistical design using a single interim look will be used for sample size re-estimation.

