4.7.1.2. Sample Size Rationale

The sample size for the study is determined under the following assumptions for the primary efficacy endpoint:

- Minimum power of 80%
- Type I error of 5%
- Assumed primary efficacy success in Treatment group: 50%
- Assumed primary efficacy success in Control group: 25%

Under the above assumptions, a minimum of 116 evaluable Subjects is required in order to demonstrate superiority of the ReActiv8 treatment. The total sample size is increased by 10% to 128 to allow for attrition.

An adaptive statistical design using a single interim look will be used for sample size re-estimation when at least 50% of the implanted Subjects have completed the Primary Endpoint Assessment Visit. Details of the interim analysis are provided in the Statistical Analysis Plan.

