6.1. Sample Size Estimate

The sample size for the study is determined under the following assumptions for the primary efficacy endpoint:

- Minimum power of 80%
- Type I error of 5%
- Assumed primary efficacy success in Treatment group: 50%
- Assumed primary efficacy success in Control group: 25%

Under the above assumptions, a minimum of 116 evaluable Subjects is required in order to demonstrate superiority of the ReActiv8 treatment. The total sample size is increased by 10% to 128 to allow for attrition. The total sample size may be increased, but not decreased, at the time of the planned interim analysis to adjust for updates to the planning assumptions.

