7.2. Missing Data and Sensitivity Analyses

The primary efficacy endpoint will be assessed in the ITT Cohort, consisting of all randomized Subjects not in the Surgical Roll In Cohort, with missing endpoint assessments examined in sensitivity analyses. Secondary efficacy endpoints will be assessed in the population of Subjects with complete data (baseline and at the Primary Endpoint Assessment Visit). Sensitivity analyses of the impact of missing data will include a tipping point analysis for the primary efficacy endpoint where the endpoint is computed with possible combinations of imputed success and failure for Subjects with missing primary efficacy assessment. Additionally, for the primary and secondary efficacy endpoints, a last observation carried forward analysis will be conducted.

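### SAP Section 5 labels 116 as the number to randomize, but 116 is the evaluable number and 128 are to be randomized; the interim trigger and the size cap need one stated basis too

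*SAP*

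**What the plan says.** **Sample size.** SAP Section 5 gives an "initial target of 116 randomized Subjects in the Intent to Treat (ITT) Cohort". SAP 6.1 says that "a minimum of 116 evaluable Subjects is required in order to demonstrate superiority of the ReActiv8 treatment" and then that "The total sample size is increased by 10% to 128 to allow for attrition". Protocol 4.7.1.2 has the same two steps. Protocol Table 1 has "Initial estimate: 128 randomized Subjects implanted with ReActiv8 in the intent to Treat cohort of the study", and Protocol 4.4 says "128 Subjects will be randomized as part of the Intent to Treat Cohort".

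**Missing outcomes.** SAP 7.2 describes the ITT Cohort as "consisting of all randomized Subjects not in the Surgical Roll In Cohort, with missing endpoint assessments examined in sensitivity analyses". It does not say how a Subject without an endpoint assessment counts in the primary comparison.

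**Interim look.** Protocol Table 1 and 4.7.1.2 time it "when at least 50% of the implanted Subjects have completed the Primary Endpoint Assessment Visit". SAP 5 has "one interim look when at least 50% of Subjects have completed the Primary Endpoint Assessment Visit" and names no denominator. SAP 8.7 uses half of the enrolment originally planned, although SAP 5 defines enrolment as the moment of consent. All versions say at least 50%.

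**Cap.** SAP 8.7 allows an increase to at most twice the designed size, written as 2 x 116, without saying whether evaluable or randomized Subjects are counted. It uses the Cui procedure for the final test but does not print the stage weights.

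**The concern.** One SAP section tells the reader to randomize 116. Another section of the same SAP, and the protocol in three places, lead to 128. Neither document has a rule saying which figure governs. SAP 5 is also the sentence that describes what approval is sought for, so someone could act on it. Stopping at 116 randomized would remove the whole attrition allowance.

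The interim wording matters for a different reason. The Cui procedure protects the Type I error only if the stage weights are fixed before interim data are seen. A trigger with an unclear base, set only as a floor, leaves room for argument about the planned fraction. The unlabelled cap matters because every added Subject has surgery.

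**Working it through.** **Inputs.** Responder rates 50% and 25%, 80% power, 5% Type I error (SAP 6.1); two-sided testing (SAP 6.2); test of two proportions (SAP 8.5.1); 1:1 allocation (SAP 5.1); 10% attrition increase (SAP 6.1).

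**1. Reproduce the plan's figure.** Pooled two-proportion z test, mean rate 0.375:

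n per arm = [1.960·√(2·0.375·0.625) + 0.842·√(0.5·0.5 + 0.25·0.75)]² / 0.25² = 57.7, rounded up to 58.

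Total 2 × 58 = 116, power 80.2%. Then 116 × 1.10 = 127.6, rounded up to 128. Both printed figures reproduce, with 116 as the evaluable number.

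**2. Effect of following SAP 5.** Power = Φ{[0.25·√n − 1.960·√(2·0.375·0.625)] / √0.4375}, with n per arm.

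- 116 randomized, 10% lost: 116 × 0.9 = 104.4, so 104 evaluable; power 75.7% (75.9% without rounding).
- 128 randomized, 10% lost: 128 × 0.9 = 115.2; power 79.9%, which meets the 80% target within rounding.
- Only the 10% rate is in the plan. At an assumed 5% or 15%, power is 78.1% or 73.4% with 116 randomized, and 82.1% or 77.6% with 128.

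These figures let Subjects without an outcome leave the denominator. If they count as failures instead, the rates at 10% become 0.5 × 0.9 = 45% and 0.25 × 0.9 = 22.5%. Power is then 73.2% with 116 randomized and 77.4% with 128. The mislabel costs about 4 points under either handling.

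**3. Effect after re-estimation.** The SAP does not say which effect its conditional power uses. I assumed the observed trend, with an increase toward 80% when conditional power is between 30% and 80%, and Cui weights of √0.5 per stage. Exact enumeration of both binomial stages gives:

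| Evaluable at design | Cap (evaluable) | Power |
|---|---|---|
| 116 | 232 | 84.2% |
| 104 | 208 | 81.9% |

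The loss is about 2 points, and power stays above 80%.

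**4. Interim fraction.** Used consistently, either base gives the same fraction: 58/116 = 64/128 = 0.5, so the weights are √0.5 = 0.707 for each stage. Different weights, √(64/116) = 0.743 and √(52/116) = 0.670, arise only if a count taken from 128 is set against 116. If the better of these two weight sets were picked after the data, one-sided error would be 2.65% to 2.69% instead of 2.50% to 2.56% (common responder rate 25% or 37.5%), a rise of about 0.1 to 0.2 points.

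**5. Unit of the cap.** 2 × 116 = 232.

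- If randomized: 232 × 0.9 = 208.8, about 209 evaluable; power 84.1%.
- If evaluable: 232 × 1.10 = 255.2, so 256 randomized (also 2 × 128); power 84.2%.

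The readings differ by 256 − 232 = 24 randomized Subjects and about 0.1 point of power.

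**The case against.** The best defence is that the correct figures are easy to find. SAP 6.1 is the sample-size section, the protocol agrees with it, and SAP Section 2 says that the two documents are read together. A careful reader would treat SAP 5 as a slip in one word. That stands, and it limits the weight of the point. It does not make the sentence right.

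Four stronger readings are tempting, and the documents do not support them.

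- *The trial is underpowered.* It is not: 116 evaluable and 128 randomized both reproduce, and the shortfall arises only if SAP 5 is followed.
- *The look must wait for half of 800 enrolled, or 400 completers.* The definition of enrolled in SAP 5 makes this possible on paper. But SAP 8.7 expresses the designed size as 116 and concerns the primary efficacy endpoint, whose primary population excludes Surgical Roll In. The word needs correcting, but 400 is not a workable reading.
- *The weights are undefined and Type I error is inflated.* Every version says 50%, and consistent use gives 0.707 per stage. Inflation would need a choice made after the data, by a third-party statistician working under the DMC. What remains is that the fraction is only a floor and the weights are not written down.
- *The maximum number of implants can be fixed by adding 80 Roll In Subjects to the cap.* Protocol 4.4 makes the 80 conditional on one implanting surgeon per site, while Table 1 allows more than one Sub-investigator at a site to implant. No firm maximum follows.

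It can also be argued that the cap means evaluable Subjects, since it serves the 80% power objective and that objective belongs to 116 evaluable. This is reasonable, but it is an inference in a sentence that SAP 5 makes ambiguous.

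**Conclusion.** The point holds as a wrong label on a sample-size figure: 116 is evaluable, 128 is the number to randomize, and SAP 5 contradicts both SAP 6.1 and the protocol. Followed literally at 10% attrition, it would take fixed-design power from about 80% to about 75.7%, or from 77.4% to 73.2% if missing counts as failure. With re-estimation as assumed here, power would be about 82% rather than 84%. The practical consequence is modest, but the figure should be corrected.

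The trigger and the cap are secondary. Their wording should be harmonized, and pre-fixing the weights avoids a possible 0.1 to 0.2 points of one-sided error. These results rest on the plan's own rates and 10% attrition; the adaptive figures also rest on the observed-trend rule, which the SAP does not state.

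**What to change.** 1. **SAP 5.** Replace 116 randomized with 128 randomized (116 evaluable) in the ITT Cohort. This costs only wording and adds nobody to the number already in SAP 6.1 and the protocol.
2. **Interim trigger.** Use one wording in Protocol Table 1 and 4.7.1.2 and in SAP 5 and 8.7, counted in ITT Subjects without Surgical Roll In. One example is 58 evaluable completers, half of 116. State that the Cui weights are fixed in advance at √0.5 per stage and kept whatever the actual count at the look. This also costs only wording.
3. **Cap in SAP 8.7.** State the unit of 2 x 116. This is a design choice for the sponsor. A cap of 232 randomized gives about 209 evaluable. A cap of 232 evaluable means about 256 randomized, a derived figure that neither document prints, and so up to 24 more randomized Subjects for about 0.1 point of power.

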5.1. Randomization

Subjects will be randomized at the Randomization Visit 14 ± 3 days post implant. Subsequent visits are scheduled relative to the date of randomization with the primary efficacy endpoint assessed at the Primary Endpoint Assessment Visit. Randomization will be performed according to a random permuted block design stratified by clinical site with a 1:1 allocation ratio for Treatment vs. Control.

5.2. Blinding (Masking)

Subjects and investigators are blinded to treatment assignment, and endpoint assessments are also blinded. An assessment of the effectiveness of the blinding procedures will be performed at the Primary Endpoint Assessment Visit.

6. Sample Size Considerations

6.1. Sample Size Estimate

The sample size for the study is determined under the following assumptions for the primary efficacy endpoint:

- Minimum power of 80%
- Type I error of 5%
- Assumed primary efficacy success in Treatment group: 50%
- Assumed primary efficacy success in Control group: 25%

Under the above assumptions, a minimum of 116 evaluable Subjects is required in order to demonstrate superiority of the ReActiv8 treatment. The total sample size is increased by 10% to 128 to allow for attrition. The total sample size may be increased, but not decreased, at the time of the planned interim analysis to adjust for updates to the planning assumptions.

6.2. Level of Power and Significance

All tests of significance will be performed at the two-sided 0.05 significance level. The hypotheses associated with the first five secondary efficacy objectives will be tested using the Hochberg multiple comparison adjustment in the event the primary efficacy objective is met.

7. Data Structure and Handling

7.1. Data Handling and Transfer

Programming of analysis datasets, tables, figures and listings will be conducted during the data management phase of the study. Tables, figures, and listings may be reviewed prior to final data lock for data review. Any data values requiring investigation or correction will be identified, and protocol deviations will be reviewed. The final run of outputs will take place after the data are deemed final.

7.2. Missing Data and Sensitivity Analyses

The primary efficacy endpoint will be assessed in the ITT Cohort, consisting of all randomized Subjects not in the Surgical Roll In Cohort, with missing endpoint assessments examined in sensitivity analyses. Secondary efficacy endpoints will be assessed in the population of Subjects with complete data (baseline and at the Primary Endpoint Assessment Visit). Sensitivity analyses of the impact of missing data will include a tipping point analysis for the primary efficacy endpoint where the endpoint is computed with possible combinations of imputed success and failure for Subjects with missing primary efficacy assessment. Additionally, for the primary and secondary efficacy endpoints, a last observation carried forward analysis will be conducted.

7.3. Visit Windows

For analysis purposes, data will be analyzed according to the visit assigned within the database.

7.4. Pooling of Data Across Trial Sites

Poolability of data will be assessed using a Mantel-Haenszel (MH) test procedure to examine the null hypothesis of a common odds ratio of responders across sites. The data will be considered poolable if the p-value for the test is ≥ 0.15 . If the p-value is < 0.15 additional analyses will be conducted to determine whether the site differences are due to imbalances in baseline factors that have evidence ($p < 0.20$) of an association with the primary outcome. These analyses may include an analysis of covariance on the percentage of pain relief, used to define responders, with site included as a random effect and adjustments for baseline covariates found to be associated with pain relief. If poolability across sites is not demonstrated, then results for the primary endpoint may be stratified and presented by site groupings.

8. Statistical Analyses

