All endpoints are assessed at 120 days post randomization (at the Primary Endpoint Assessment Visit).

Compliance with instructions for stimulation delivery will be assessed from data stored in the ReActiv8 IPG, which records the start and stop time of each stimulation session.

The Primary Efficacy Endpoint is a comparison of responder rates of pain where a “responder” is a Subject with $\geq 30\%$ reduction from baseline in average low back pain VAS, without any increase in pain medication and/or muscle relaxants prescribed and taken in the two weeks prior to the Primary Endpoint Assessment Visit.

Several secondary endpoints will be assessed, including change in ODI, change in EQ-5D Quality of Life, change in Percent Pain Relief, and Subject Global Impression of Change, all assessed as a difference between baseline and the Primary Endpoint Assessment Visit.

a In this Clinical Investigation Plan, the term used is “subject” instead of “patient” in line with the suggestions of ISO 14155. The terms should be considered as synonymous.

Subgroups will be also analyzed based on Subject characteristics (e.g.: BMI) and by site. Several other endpoints will be analyzed on an exploratory basis.

Safety will be assessed by collecting data on the rate of all serious device and/or procedure related adverse events in all enrolled Subjects. Adverse event data will be collected at each visit beginning with the Baseline Visit. The Safety Cohort consists of all enrolled Subjects in whom implant was attempted or successful. A separate analysis will be conducted of the Safety Cohort without Subjects included in the Surgical Roll In Cohort.

Table 1: Synopsis of Clinical Investigation

Study Purpose	To evaluate the safety and efficacy of ReActiv8 for the treatment of adults with Chronic Low Back Pain and no prior spine surgery when used in conjunction with medical management.
Indication For Use	ReActiv8 is an adjunct to medical management in adults with Chronic Low Back Pain for relief of pain in subjects who have failed at least medical management and physical therapy.
Study Device	Mainstay ReActiv8
Study Design	International, multi-center, prospective, randomized, sham controlled, blinded Trial with an adaptive statistical design. Subjects are blinded, investigators are blinded, and the assessment of primary endpoint data is blinded.

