8.2. Study Populations

Several Cohorts are defined.

Intent to Treat (ITT) Cohort consists of all randomized Subjects who are not in the Surgical Roll-In group. This is the primary analysis population for the primary efficacy endpoint. The primary efficacy endpoint will be assessed in the ITT cohort. Additionally, the following analysis populations are defined. The primary efficacy endpoint will also be assessed in the per-protocol and completer cohorts. The secondary efficacy endpoints will also be assessed in the ITT cohort.

Surgical Roll In Cohort consists of all Subjects implanted in the Surgical Roll In group.

Per-protocol: Subjects within the ITT cohort receiving the correct randomized treatment, meeting the enrollment criteria, compliant with delivery of stimulation at least 80% of the maximum possible sessions delivered, and who have no other major protocol deviations affecting the primary endpoint evaluation will be considered to be part of the Per Protocol population.

Completers: All randomized Subjects who complete the Primary Endpoint Assessment Visit and associated endpoint assessments, regardless of compliance with the delivery of stimulation or the requirement to maintain constant medications.

Crossover Cohort: All Subjects in the Crossover Group who met the inclusion criterion 2 for low back pain (Low Back Pain VAS of ≥ 6.0 cm and ≤ 9.0 cm (on a 10cm scale)) and inclusion criterion 3 for ODI (Oswestry Disability Index score $\geq 21\%$ and $\leq 60\%$) at the time of crossover.

The primary efficacy endpoint and secondary efficacy endpoints will also be assessed in the Per-protocol and Completer cohorts.

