8.5. Primary Efficacy Endpoint

8.5.1. Primary Analysis

The Primary Efficacy Endpoint is a comparison of responder rates between Treatment and Control groups, where a “responder” is a Subject with $\geq 30\%$ reduction from baseline in average low back pain VAS, without any increase from baseline in pain medication and/or muscle relaxants prescribed and taken in the two weeks prior to the Primary Endpoint Assessment Visit.

Note: The primary outcome measure is intended to assess the efficacy of 120 days of stimulation. Thus the visit for assessment of the primary outcome must occur no sooner than 120 days post randomization.

The primary efficacy endpoint will be assessed by the following hypotheses:

$H_0: \pi_{VAS_T} = \pi_{VAS_C}$

$H_A: \pi_{VAS_T} \neq \pi_{VAS_C}$,

where π_{VAS_T} is the proportion of Subjects meeting primary success criteria in the Treatment group and π_{VAS_C} is the proportion of Subjects meeting success criteria in the Control group. The hypotheses will be tested using a two-sided binomial test for a difference in proportions. The objective will be met if a statistically significant difference favoring the Treatment group is found.

The study will be considered a success if the primary efficacy endpoint is met.

For the primary analysis in the ITT population, the impact of Subjects with missing endpoint assessment will be examined in sensitivity analyses.

Records of pain medications will be collected along with all other medications used for treatment of low back pain, which are also being collected for analysis of secondary and cost-effectiveness endpoints. The Subject will report medications taken at each scheduled follow-up visit. Rescue medications taken on an exceptional basis for acute pain conditions other than back pain will also be documented and their possible effect examined as part of sensitivity analyses.

The number and percent of randomized Subjects meeting the responder criteria will be presented by randomization group with associated 95% asymptotic confidence limits. The difference in proportions and associated 95% confidence limits will be presented along with the p-value from a binomial test for the test of the hypothesis associated with the primary objective.

The individual components of the primary efficacy endpoint (VAS and medications) will be analyzed and presented separately. Cumulative proportion of responder analysis will also be used as a way of presenting this data.

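### SAP 7.4 names a Mantel-Haenszel test for a null it does not test; run as named, a device with the planned effect at every site misses the poolability threshold in about 9 of 10 trials

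*SAP*

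**What the plan says.** SAP 7.4 has three steps.

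1. Poolability is "assessed using a Mantel-Haenszel (MH) test procedure to examine the null hypothesis of a common odds ratio of responders across sites". The decision threshold is 0.15, and sites pass at or above it: "The data will be considered poolable if the p-value for the test is" at least that value.
2. Below 0.15, "additional analyses will be conducted to determine whether the site differences are due to imbalances in baseline factors" associated with the outcome. A covariance analysis of percentage pain relief, with site as a random effect, is given as a possibility.
3. "If poolability across sites is not demonstrated, then results for the primary endpoint may be stratified and presented by site groupings".

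SAP 5 plans recruitment "in up to 40 implanting sites to achieve an initial target of 116 randomized Subjects in the Intent to Treat (ITT) Cohort". Of the ITT cohort, SAP 8.2 says: "This is the primary analysis population for the primary efficacy endpoint". Of the primary hypotheses, SAP 8.5.1 says: "The hypotheses will be tested using a two-sided binomial test for a difference in proportions". Protocol 2.4 adds: "Subgroups will be also analyzed based on Subject characteristics (e.g.: BMI) and by site". The list of subgroups in SAP 8.11 does not name site.

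**The concern.** The null in 7.4 is homogeneity: the same odds ratio at every site. The named test has a different null, namely that an odds ratio common to all sites equals 1. A programmer must either run the named test, which answers the wrong question, or substitute one the SAP does not name.

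Run as named, the rule works nearly backwards. A device that works equally well everywhere produces a small p-value and misses the threshold. A device that does nothing, or helps at some sites and harms at others, tends to pass. The follow-up analyses of site differences would then be looking at the treatment effect itself.

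If a homogeneity test was meant, the usual choice is Breslow-Day. Its chi-square reference needs adequate counts per site, and 116 subjects over 40 sites is 2.9 per site.

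Two further gaps leave room for choices after the data are seen. The site groupings are not defined in advance, and 7.4 does not say which result of the covariate step means that poolability has failed. Apart from this rule, the SAP specifies no check that the effect agrees across sites.

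**Working it through.** **Inputs from the SAP.** Responder rates 50% and 25%, 80% power, 5% type I error and 116 evaluable subjects (6.1); two-sided testing (6.2); 1:1 permuted blocks stratified by site (5.1); up to 40 sites (5); at most 2 x 116 = 232 subjects after re-estimation (8.7). The planned odds ratio is (0.50/0.50)/(0.25/0.75) = 3.0.

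**Assumptions not in the documents.** Blocks of 4; 10, 20 or 40 sites, all active; equal baseline rates across sites; site sizes equal to within one subject, or multinomial (random).

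**Reproducing 116.** With mean rate 0.375, n per arm = [1.960 x sqrt(2 x 0.375 x 0.625) + 0.842 x sqrt(0.25 + 0.1875)]^2 / 0.25^2 = (1.342 + 0.557)^2 / 0.0625 = 57.7, rounded up to 58. The total is 116, as stated (power 80.2%).

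**MH test, normal approximation.** For site i, with a_i treatment responders, n1_i and n2_i subjects per arm, t_i responders and N_i subjects:

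- E_i = n1_i t_i / N_i
- V_i = n1_i n2_i t_i (N_i - t_i) / [N_i^2 (N_i - 1)]
- MH chi-square = [sum(a_i - E_i)]^2 / sum(V_i), on 1 df

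The numerator adds signed differences. A uniform effect accumulates and opposite effects cancel, so the statistic measures association, not heterogeneity. Ignoring stratification, with 58 per arm and a two-sided 0.15 cut-off (z = 1.440):

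P(p < 0.15) = Phi[(0.25 - 1.440 x sqrt(0.46875/58)) / sqrt(0.4375/58)] = Phi[(0.25 - 0.1294)/0.0869] = Phi(1.39) = 0.917.

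**Simulation, 116 subjects, equal site sizes.** The reversed case is 50% versus 25% at half the sites and 25% versus 50% at the rest. Breslow-Day uses the number of informative sites minus 1 as degrees of freedom. Zelen's test conditions on all margins and the responder total.

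| Test and truth | Result | 10 sites | 20 sites | 40 sites |
|---|---|---|---|---|
| MH, odds ratio 3.0 everywhere | p < 0.15 | 92% | 91% | 89% |
| MH, no effect anywhere | p < 0.15 | 15% | 15% | 15% |
| MH, effect reversed | p >= 0.15 | 87% | 87% | 87% |
| Breslow-Day, odds ratio 3.0 everywhere | p < 0.15 | 20% | 28% | 73% |
| Zelen, odds ratio 3.0 everywhere | p < 0.15 | 15% | 14% | 10% |
| Zelen, effect reversed | p < 0.15 | 63% | 48% | 27% |

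**Sensitivity.**

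- Random site sizes: MH 88-92%; Breslow-Day 20%, 32%, 56%; Zelen 15%, 15%, 14%.
- MH with continuity correction, 5 to 40 sites: 85-89%. At 128 subjects without correction: 92-94%.
- Baseline logit SD 0.7 between sites: MH 90%, 89%, 85%; Breslow-Day 19%, 27%, 70%; Zelen 15%, 13%, 9%.
- Tarone-adjusted Breslow-Day at 116 or 128 subjects: 17-19% at 5-10 sites, 26-28% at 20, 61-68% at 40.
- 232 subjects, 40 sites: MH 99%; Breslow-Day 40-42%; Zelen 15-16%.
- Smaller uniform effects, MH, 116 subjects, 10-40 sites: 76-80% for 45% versus 25%; 58-62% for 40%; 38-40% for 35%.
- Zelen on sites merged to at least 16 subjects: power 11-16% against reversal. With log odds ratio SD 1 between sites, 33%, 23%, 16% merged against 51%, 38%, 17% on single sites.

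**The case against.** The strongest reply is that the stated null and the follow-up on site differences both describe homogeneity, so a sensible analyst would run a homogeneity test and the 9-in-10 result would never arise. That is fair as to intent, and the figure does depend on running the test as named. But the SAP names no homogeneity test for sites, and the usual one over-rejects when sites are small.

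Other points also have force:

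- The 9-in-10 figure holds at the planned effect and falls with smaller effects, as shown above.
- The severe Breslow-Day figure needs all 40 sites to contribute ITT subjects. Forty is a ceiling, and at 10 sites the excess is mild.
- Full reversal is extreme. Both arms then average 37.5%, and the primary test significantly favours Treatment in only about 2% of such trials, so a false poolable verdict would rarely accompany a positive trial.
- The 8.11 list is a stated minimum, and SAP 2 has the SAP read alongside the protocol, so analysis by site is not dropped. It is left without a specified method.
- Zelen's test is not the only option, since a pre-specified site-by-treatment model is another, and its power at 40 sites is low.

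These points limit the consequences. They do not make the named test fit its null or make the 0.15 rule reliable.

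**Conclusion.** The concern holds. The mismatch between test and null is plain from the text and needs no simulation. Run as named, at 116 subjects and 50% versus 25% at every site, the rule sends about 9 in 10 trials to further analysis, and it passes 87% of trials in which the effect fully reverses between sites. Read as Breslow-Day, it raises false alarms in 20% to 73% of trials against a nominal 15%, depending on the number of sites. These sizes rest on the assumed site numbers, site sizes and block size.

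The primary binomial test, its p-value and the success criterion do not depend on poolability. The damage is to the poolability conclusion and to how the primary result may be presented. This should be corrected, but it does not threaten the primary inference.

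**What to change.** In SAP 7.4:

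1. Replace the MH test with Zelen's exact test of equal odds ratios on individual sites, keeping the 0.15 threshold. Do not run it on merged sites: merging averages opposite effects away, and single-site power was at least as high in every setting examined.
2. Before unblinding, fix the site groupings by a stated minimum size, for use only in a stratified presentation.
3. Report a p-value of 0.15 or more as no evidence of heterogeneity, not as proof of poolability.
4. As clarifications, state which result of the covariate step means that poolability is not shown, and that the pooled ITT result stays primary whatever the test shows, with by-group results supportive.

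The cost is a few sentences and minor programming. Groupings can no longer be chosen later. No heterogeneity test will be powerful with so few subjects per site: Zelen's detects a full reversal in only 27% of trials at 40 sites.
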